4.9 Staging, Gleason score and Gleason Grade Group

Staging, Gleason score and categorization will be analyzed using the FAS.

TNM staging at baseline (pathological or clinical if no pathological available) will be summarized by type. In addition, a summary by center will be provided.

TNM staging will be listed by patient and center.

Parexel International

Blue Earth Diagnostics Ltd
BED-PSMA-302

Statistical Analysis Plan

Frequency of total Gleason score will be summarized, using score from surgery as primary result and biopsy if no surgery available. Scores below 6 will be combined to a score of ≤ 6 in summary tables. Primary, secondary and total Gleason scores will be listed by patient and center.

Gleason Grade Group is defined by the International Society of Urological Pathologists, and the categories are as follow:

- Grade Group 1 is defined as Total Gleason score ≤ 6
- Grade Group 2 is defined as Gleason score $3+4=7$
- Grade Group 3 is defined as Gleason score $4+3=7$
- Grade Group 4 is defined as Total Gleason score of 8
- Grade Group 5 is defined as Total Gleason scores 9-10

Gleason Grade group (using surgery or biopsy if no surgery is available) will be summarized.

For any analysis by TNM stage, pathologic will be used, while clinical will be used if no pathologic is available. For any analysis by Gleason Grade group or Gleason Score the surgery Gleason will be used while biopsy will be used if no surgery is available. TNM staging will be displayed at observed level and combined at levels T2, T3, T4, M0, M1, MX, where each of these contain underlying categories (i.e. T2 -All contains subjects with observed at T2, T2a, T2b, T2c)

4.10 PSA

PSA will be analyzed using the FAS.

Most recent PSA level will be summarized as a continuous variable.

An additional summary of PSA level will be by prior therapy based on PT. Each patient will be in one category only.

- Prior Prostatectomy (as defined in section 4.8). This includes all patients who had other therapies (including radiotherapy), as long as they had prostatectomy.
- Prior Radiation Therapy (as defined in section 4.8). This excludes patients with previous prostatectomy.
- Other: Neither Radiation Therapy nor Prostatectomy.

A plot (spaghetti plot) showing subject PSA against Study Day (relative to PET scan) by center. PSA will be listed by patient date, and study day, with a cut-off of two years (day -730).

In addition, PSA will be categorized using the categories: $PSA < 0.5$, $0.5 \leq PSA < 1.0$, $1.0 \leq PSA < 2.0$, $2.0 \leq PSA < 5.0$, $5.0 \leq PSA < 10.0$, $10.0 \geq PSA$ (ng/mL). A frequency table of the categories with proportion will be provided overall. These same categories will be used for analysis of subgroups on PSA level. In case of categories with low counts a category may be merged with an adjacent category in order to have at least five patients in each category.

The PSA doubling time will be calculated by first doing regression of historical natural log PSA on date of PSA measurement and subsequently division of natural log 2 (0.693) by the slope, using the last 3 values in the 2 years prior to PSMA dosing in the model. A month is assumed to take 30.5 days. In case there are not 3 acceptable measurements in the prior 2 years then no doubling time will be provided. Negative slopes will be missing in summaries.

Parexel International

Blue Earth Diagnostics Ltd
BED-PSMA-302

Statistical Analysis Plan

In case of incomplete dates for PSA measurement, for the doubling time calculation the date may be imputed or the measurement may be ignored, based on the following rules:

- If the day part is missing but the month and year are known, then the 15th of the month will be used.
- If the day and month parts are missing, then the PSA measurement will be ignored.

In case of less than PSA values (e.g. '<0.1') the numerical value will be used after removal of the '<' character.

PSAdt will be categorized using the categories PSAdt<6, 6≤PSAdt<12, 12≤PSAdt<24, 24≤PSA (months) and not estimable (for non changing and decreasing PSA [slope <=0]). This same categorization will be used for the analysis of subgroups on PSAdt.

All PSA results (including a flag if PSA is used for the PSAdt calculation) and all PSAdt, slope, number of points used and date range used [dates and duration {months}] will be listed by patient, center and date.

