6.2 Inclusion Criteria

1. Patient willing to provide signed informed consent and willing to comply with all required study schedule events, where safe and feasible.
2. Patient is male and aged >18 years old.
3. Patient with a history of localized adenocarcinoma of the prostate with prior curative intent treatment, experiencing BCR of PCa potentially eligible for salvage therapy with curative intent, following prior treatment with one or more of the following: a) RP, b) RP plus adjuvant RT, c) RP plus adjuvant androgen deprivation therapy (ADT), d) external beam radiation therapy or e) focal gland therapies (e.g. brachytherapy, high-intensity focused ultrasound [HIFU]).

- At least 6 weeks must have elapsed after RP.
- If previously taking ADT, it should have been discontinued at least 16 weeks prior to screening.
- In the case of focal gland therapies (e.g. HIFU) and RT, the treatment will have occurred at least 1 year prior to screening.

4. An elevated PSA, clinically suspicious for biochemically recurrent disease, that meets one of the following conditions:

- Following RP with or without adjuvant or salvage therapy: PSA ≥ 0.2 ng/mL followed by a subsequent confirmatory PSA value ≥ 0.2 ng/mL.
- Following RT (e.g. radical radiotherapy or brachytherapy) as the primary treatment: nadir +2 ng/mL.
- Following focal gland therapy (e.g. HIFU) as the primary treatment: nadir +2 ng/mL.

5. Patient willing to undergo biopsy for histological confirmation of rhPSMA-7.3 (^{18}F) PET findings, where safe and feasible.

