4.16.4.5 Patient and regional level detection rates of rhPSMA-7.3 (¹⁸F) PET as a function of PSA, prior Gleason score and PSAdt in a) post-RP; b) post-RT patients.

This concerns patients in subgroups of the EPSP with an extra subgroup condition, for a) the patient has had RP, for b) the patient has had RT (see Section 4.8). The regions analysis will concern local

Parexel International

Blue Earth Diagnostics Ltd
BED-PSMA-302

Statistical Analysis Plan

recurrence, pelvic lymph nodes and other. Patients will be analyzed by PSA category (Section 4.10), by total (biopsy and surgery) Gleason score (Section 4.9) and by PSAdt category (Section 4.10) for each of the blinded readers and their majority.

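### PSA doubling time enters a '<x' result as x, which lengthens PSAdt by an amount set by the local reporting limit when that value is the earliest of the three

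*SAP*

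**What the plan says.** SAP 4.10 regresses the natural log of PSA on measurement date, "using the last 3 values in the 2 years prior to PSMA dosing in the model", followed by "subsequently division of natural log 2 (0.693) by the slope". A result carrying a less-than sign is not treated as censored: "the numerical value will be used after removal of the" sign. The SAP's own example is '<0.1'.

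On minimum data it says "In case there are not 3 acceptable measurements in the prior 2 years then no doubling time will be provided", but it does not state whether a '<' result is acceptable. PSAdt is then cut at 6, 12 and 24 months, with a further 'not estimable' category that the SAP defines as a slope of zero or less. "This same categorization will be used for the analysis of subgroups on PSAdt".

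That subgroup use is SAP 4.16.4.5 (exploratory endpoint 5), where detection rates after prostatectomy and after radiotherapy are shown "by PSAdt category (Section 4.10) for each of the blinded readers and their majority".

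**The concern.** A result of '<0.1' says only that PSA lies somewhere below 0.1. The rule enters it in the regression as if 0.1 had been measured.

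Protocol 6.2 shows where such a value will usually fall. Entry after prostatectomy needs a PSA of at least 0.2 ng/mL "followed by a subsequent confirmatory PSA value" that is also at least 0.2. Two of the last three values are therefore normally quantified, and a '<' value, if there is one, is normally the earliest. In that position the substitution acts in one direction: it lengthens PSAdt. The amount depends on the reporting limit. The documents set no common limit: Protocol 9.3 provides for no study laboratory measurements, and up to about 35 sites take part.

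At stake is the PSAdt category. A man whose PSA is doubling fast can be placed in a slower category, which may distort the baseline description and the pattern of detection by PSAdt.

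**Working it through.** No sample size, power or alpha figure depends on this rule, so there is no design figure to reproduce. The one constant it uses, ln 2 = 0.693, is correct.

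**Direction.** The least-squares slope is Σ(tᵢ − t̄)·ln yᵢ / Σ(tᵢ − t̄)². The earliest date lies below the mean date, so ln y₁ has a negative weight. Raising y₁ from its true value to the limit L therefore always lowers the slope. Since PSAdt = ln 2 / slope, PSAdt rises. When only the earliest value is below the limit, the SAP's result is an upper bound on the PSAdt that the true concentrations would give.

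**Example** (PSA values and dates assumed): '<L', 0.2 and 0.4 ng/mL at 0, 9 and 18 months. With equal spacing the slope reduces to ln(y₃/y₁)/18.

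| First value entered | ln(0.4/y₁) | Slope per month | PSAdt (months) | Category |
|---|---|---|---|---|
| 0.1 (SAP rule for '<0.1') | 1.386 | 0.0770 | 9.0 | 6 to <12 |
| 0.02 (possible true value) | 2.996 | 0.1664 | 4.2 | <6 |
| 0.01 (possible true value) | 3.689 | 0.2049 | 3.4 | <6 |

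Other assumed patterns show the range. For a first value, then 0.20 and 0.25 at 0, 12 and 18 months, entering 0.1 gives 13.4 months and entering 0.01 gives 3.7, two categories apart. For a first value, then 0.5 and 1.0 at 0, 6 and 12 months, the results are 3.6 and 1.8, both in '<6'.

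**How often the category is wrong among affected men.** Assumptions, none from the documents: exact log-linear growth, true PSAdt uniform from 2 to 24 months, last PSA uniform from 0.2 to 1.5 ng/mL, and three random dates within 24 months at least one month apart. Only men with the first value below the limit and the other two at or above 0.2 are kept.

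| Limit (ng/mL) | Men kept | Median of SAP PSAdt / true PSAdt | Category wrong |
|---|---|---|---|
| 0.1 | 2,072 | 1.30 | 28% |
| 0.05 | 929 | 1.24 | 9% |
| 0.01 | 160 | 1.16 | 0% |

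A second run under assumed log-linear growth gave 26%, 7% and 0%. No PSAdt came out shorter than the truth in the tabulated run.

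**Using the result as a bound.** Without assay noise, every man assigned to '<6' because his bound was below 6 months truly belonged there. With 10% assay noise at least 99% did.

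**The case against.** The rule is simple, prespecified and deliberate: the SAP revision history lists it among the version 3.0 changes. SAP 4.10 also lists every PSA result with a flag for those used, so affected men can largely be traced. PSAdt enters no hypothesis test, SAP 4.16.1.5 rules out covariate adjustment in the primary analysis, and the secondary stratification uses the last PSA level. All of this stands and limits the point to a minor one.

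The worked example is also open to challenge. The two quantified values, 0.2 and 0.4 nine months apart, themselves double in 9.0 months, which is the SAP's answer. A true first value of 0.02 implies a tenfold rise in the first nine months and a slower one afterwards. That is fair: the example shows what the same regression would return on the true values, not a log-linear course. The direction rests on the regression weights and does not need the example. The lengthening is also relative to that comparator. Against the slope through the two quantified values alone, substitution can shorten PSAdt: for '<0.1', 0.20 and 0.25 at 0, 6 and 12 months it gives 9.1 months against 18.6.

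Three stronger readings are tempting, and the documents do not support them.

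- That many men are affected. No count is given. Entry after radiotherapy or focal therapy requires nadir +2 ng/mL, and about 60% of patients are planned at PSA of at least 1 ng/mL, so many may have three quantified values.
- That the detection gradient is reversed. Men with a recent undetectable value probably have low PSA, where detection is lower (58% below 1 ng/mL against 97% at 2 or more in Protocol 1.2). Moving them to slower categories could equally exaggerate the expected gradient.
- That PSAdt is always too long. If a '<' value is the middle point, or limits differ between draws, the direction can reverse: true values 0.008, 0.02 and 0.2 at 0, 15 and 18 months give 4.9 months, while '<0.01', '<0.1' and 0.2 give 4.3. The entry rule makes this unlikely.

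**Conclusion.** The point holds as a minor flaw in a derivation rule. When a '<' value is the earliest of the three points, the SAP's PSAdt exceeds what the true concentrations would give, by an amount that depends on the local reporting limit. That direction is algebraic. The size is not: under assumed log-linear growth the category is wrong in roughly a quarter of affected men at a limit of 0.1, under 10% at 0.05 and none at 0.01. The SAP names only '<0.1'; the other limits are illustrations, and the share of men affected is unknown.

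The reach is the baseline PSAdt summary and exploratory endpoint 5, where misclassification may distort the detection-by-PSAdt pattern in a direction that cannot be stated in advance. A reader might infer a threat to the trial's conclusions; there is none, because the co-primary CDR and PPV analyses and the sample size do not use PSAdt.

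**What to change.** In SAP 4.10:

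1. State that '<' values are not acceptable measurements, and calculate PSAdt from the last three quantified values in the 2 years before dosing. Add that reaching back past a '<' value must not bring in a PSA from before the prior curative treatment. The window can contain one, since Protocol 6.2 allows entry 6 weeks after prostatectomy.
2. If fewer than three such values exist and the earliest of the last three is the '<' value, use the current calculation only as an upper bound. Assign '<6 months' if the bound is below 6.
3. Otherwise report the man in a separate row, such as 'not calculated: value below reporting limit'. Do not put him in 'not estimable', which the SAP reserves for a flat or falling PSA.
4. Report how many men fall under steps 2 and 3.

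A left-censored fit for each man is not a workable alternative. With two quantified points and one censored point, the likelihood is unbounded whenever the line through the two quantified values reaches or falls below the limit at the earliest date. In the '<0.1' example it tends to 9.0 months, which is the current answer.

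The cost is a few sentences and a small derivation change. The downside is that some post-prostatectomy men with recent recurrence will have no PSAdt category.

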4.11 Biopsy/Surgery

If rhPSMA-7.3 (¹⁸F) PET shows one or more sites of recurrence, the most accessible and feasible (as judged by the local investigator) lesion(s) will be biopsied under radiological guidance. In patients with multiple rhPSMA-7.3 (¹⁸F) PET-positive regions, attempts should be made, where safe and medically feasible, to obtain histopathology on the most accessible and feasible lesion(s) in each region (prostate bed, pelvic lymph nodes, and other [bone, extra-pelvic lymph nodes, soft tissues/parenchyma]).

In cases where a patient will undergo a lymph node dissection or other surgical procedure (resection of the PET-positive lesion(s)) as part of their standard of care, a biopsy prior to the surgical procedure is not required. The histology obtained following surgery will serve as the SoT. The removed surgical samples will be carefully correlated to rhPSMA-7.3 (¹⁸F) PET and the conventional imaging technique(s).

Biopsy/Surgery will only be analyzed in the context of efficacy endpoints.

A listing of Biopsy/Surgery including histopathology results will be provided by subject, region and lesion. PET positive lesions for which no biopsy is performed will not be listed.

4.12 Conventional Imaging

4.12.1 Baseline Conventional Imaging

Baseline standard of care conventional imaging may include: planar and/or single-photon emission CT bone scan (^{99m}technetiumhydroxydiphosphonate [^{99m}TcHDP], ^{99m}technetium-methyldiphosphonate [^{99m}TcMDP] per institution preference), abdominal/pelvic CT or MRI, chest CT per institution preference, or PET with (¹⁸F-NaF or Axumin). Baseline conventional imaging that has been performed within 90 days prior to enrollment at non-participating institutions will be accepted (when available) provided the scans are reviewed by the participating institution.

Parexel International

Blue Earth Diagnostics Ltd
BED-PSMA-302

Statistical Analysis Plan

If not already completed within the 90 days before enrollment, baseline standard of care conventional imaging will be performed at the study site, between Visit 1 and up to 2 weeks following the rhPSMA-7.3 (¹⁸F) PET scan according to site standard of care. Any conventional imaging performed up to 90 days prior to Visit 1 and up to and including Visit 2(a) will be considered baseline conventional imaging.

Baseline conventional imaging will be listed including modality, and imaging result for each scan performed.

Baseline conventional imaging result will be summarized by modality and overall using the FAS. Conventional imaging methods which are infrequently used may be combined for summary purposes, based upon the judgement of the Biostatistician. In case of replication of modality within a subject, a negative will be counted if all results are negative while a positive will be counted if any result is positive.

4.12.2 Historical Conventional Imaging

Historical conventional imaging acquired more than 90 days before Visit 1, if available and if performed as part of the patient's PCa staging and treatment in the prior ~24 months, can be used along with baseline conventional imaging to establish SoT where a biopsy cannot be obtained.

Patients will be asked to provide these pre-existing images to the study site, if these were done at another institution. If done at the study site, these images will be made available by the study site. Historical conventional imaging will be listed by date and modality. Imaging results of historical conventional imaging will only be utilized in the determination of SoT.

4.12.3 Confirmatory Imaging

In cases where baseline and historical (when available) conventional imaging are inconclusive for SOT determination, rhPSMA-7.3 (¹⁸F) directed (for confirmation of lesion location only) follow-up confirmatory imaging of the site(s), will be acquired at the discretion of the local investigator(s), with reference to the Study Imaging Manual. Examples of confirmatory imaging modalities include specific body region MRI (including functional or multi-parametric MRI), CT, Axumin, ¹⁸F-NaF, etc. Confirmatory imaging will be listed by date, modality and anatomical location. Imaging results of confirmatory imaging will only be utilized in the determination of SoT.

4.13 Exposure and Treatment Compliance

A subject listing of rhPSMA-7.3 (¹⁸F) treatment including total administered activity, injection site reactions, local imaging results, incidental findings, clinical review and evaluations of independent blinded central PET readers will be provided.

A summary of total administered activity will be provided using the FAS and PP. All activity will be shown in MBq and mCi using the conversion 1mCi=37 MBq.

Parexel International

Blue Earth Diagnostics Ltd
BED-PSMA-302

Statistical Analysis Plan

4.14 rhPSMA-7.3 (¹⁸F) Image reading

Each rhPSMA-7.3 (¹⁸F) image will initially be read by a site-based local reader. In addition, for the primary endpoint analysis, imaging will be read by three blinded independent PET readers (see the study Independent Review Charter for further details). The results of the blinded PET readers will be used in the primary analysis, thus requiring each (statistical) analysis to be performed three times. In addition, the majority interpretation will be displayed.

Majority will be determined on both a region and patient level. The region level majority looks at the region level decision by the blinded independent PET readers within each region, independent of anatomical location within the region. Thus, if two or three readers identify a positive lesion within a region, the majority for the region will be positive. In addition, if SoT panel confirms a positive lesion, the majority would be TP, otherwise majority would become FP. The patient level analysis will ignore region, meaning that if two or three readers find any positive lesion for a patient, the majority for the patient will be positive.

Table 5: Derivation of Overall Interpretation (2 out of 3 readers majority)

Reader 1	Reader 2	Reader 3	Majority
Positive	Positive	Positive	Positive
Positive	Positive	Negative	Positive
Negative	Negative	Positive	Negative
Negative	Negative	Negative	Negative

PET imaging results (i.e. positive/negative) will be summarized using EPSP by anatomical location by category and anatomical location within category. Categories will be prostate, pelvic lymph nodes, lymph nodes outside of pelvis, soft tissue/parenchyma and bones. All categories will be presented in the summary, but anatomical locations will only be presented where data are collected, i.e. lesion investigated in that anatomical location.

Any PET scan reads by additional independent central PET readers who do not complete the full set of reads will be listed only.

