*Note: in addition to patient safety, assessment of feasibility may include location, but also lesion size, where a minimum size may be needed to avoid excessive sampling error on biopsy; soft tissue lesions will be preferred over bone lesions due to the higher likelihood of non-diagnostic bone biopsies ([Didolkar 2013](#); [Yang 2010](#)).

In cases where a patient will undergo a lymph node dissection or other surgical procedure (resection of the PET-positive lesion(s)) as part of their standard of care, a biopsy prior to the surgical procedure is not required. The histology obtained following surgery will serve as the SoT. The removed surgical samples will be carefully correlated to rhPSMA-7.3 (¹⁸F) PET and the conventional imaging technique(s).

In cases where a biopsy is not feasible or refused by the patient, then specific imaging may be used, to confirm positivity of the finding on rhPSMA-7.3 (¹⁸F) PET (see below Steps 2 to 4; [Sections 9.2.2.1, 9.2.2.2](#) and [9.2.2.3](#)). Histopathology remains the preferred SoT.

9.2 *SoT*

One of the following will determine SoT: If a positive lesion on PET is confirmed by one of the Steps (1 to 4) listed below, the lesion will be considered TP. When determining the CDR on a patient level, a patient will be categorized as a TP if there is at least one TP lesion confirmed in one body region (prostate bed, pelvic lymph nodes, or other extra-pelvic sites [bone, viscera, lymph nodes and soft tissues]) on rhPSMA-7.3 (¹⁸F) PET. For the primary analysis, pelvic lymph nodes will include the right and left external iliac, obturator, hypogastric (internal iliac), perirectal and presacral lymph node groups.

Notes:

- a. In patients with multiple PET-positive regions, confirmation of at least one PET-positive lesion in each region is required either by biopsy/surgical resection or confirmatory imaging in order to calculate the region level PPV for the efficacy analyses.
- b. In patients with multiple lesions in a specific region, the presence of one TP lesion determines truth for the region regardless of any concurrent FP findings in the same region.

Therefore, multiple PET-positive lesions can be evaluated in a specific region in order to confirm at least one TP.

9.2.1 *Step 1: Histological SoT*

Histological confirmation, whenever possible:

- a) Of PET-positive lesion.
- b) Of surgically removed sample.
- c) Re-biopsy (in case of inconclusive histology) or biopsy of a second lesion will be allowed.

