3.2.2.2 Step 3: Confirmatory Imaging SoT (up to 45 Days Post-rhPSMA-7.3 (¹⁸F) PET)

In cases where, in the opinion of the local site reader, historical conventional images are not available or are inconclusive in comparison to baseline imaging, rhPSMA-7.3 (¹⁸F) directed (for confirmation of lesion location only) follow-up confirmatory imaging of the site(s), will be acquired. Confirmatory imaging will be acquired at the discretion of the local investigator(s), with reference to the Technical Operations Manual.

3.2.2.3 Step 4: Additional Confirmatory Imaging SoT (up to 90 Days Post-rhPSMA-7.3 (¹⁸F) PET)

If in the opinion of the local investigator(s) the above imaging Steps 2 or 3 do not allow SoT verification, then a final follow-up, rhPSMA-7.3 (¹⁸F) PET directed (for confirmation of lesion location only) confirmatory imaging scan can be obtained up to 90 days post rhPSMA-7.3 (¹⁸F) PET.

Reading of conventional and confirmatory imaging to determine the next steps in the confirmation process will be performed locally.

Both the rhPSMA-7.3 (¹⁸F) PET scans and all available conventional (historical and baseline) and confirmatory imaging scans acquired under Steps 2 to 4 above will be read centrally for the primary endpoint assessment, according to [Table 1](#) and [Figure 1](#) below. Reads of the conventional and confirmatory imaging as SoT will be directed by rhPSMA-7.3 (¹⁸F) PET findings (for confirmation of lesion location only) and performed by different readers than the blinded, independent rhPSMA-7.3 (¹⁸F) interpretations. Three central reviewers will review all submitted images and reach consensus on the nature of the PET positive target lesion(s). A brief summary of clinical information will be made available to the readers (e.g. 67-year-old male post-RP with pelvic lymph node dissection (PLND) and adjuvant pelvic RT 5 years before; PSA rising to 1.2 ng/mL prior to rhPSMA-7.3 (¹⁸F) scan; PSA_{Adt} 9 months). Readers will be blinded to all other information. Further details are given in the study Independent Review Charter.

rhPSMA-7.3 (¹⁸F) positive lesions will be categorized by the consensus central SoT read as positive, negative or indeterminate using all available conventional and confirmatory imaging. Indeterminate classifications will be categorized as False Positives for the primary analysis. Further details are given in the study Independent Review Charter.

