Central read of SoT involving the blinded independent PET readers who did not complete the full set of rhPSMA-7.3 (¹⁸F) PET reads will only be listed.

The imaging SoT will be matched with the blinded PET reader based on the lesion ID for each reader as identified by the SoT panel, and the histopathology finding by the investigator (as recorded on CRF) will be matched with the blinded PET reader finding based on the anatomical location of the lesion. Histopathology finding will only be used if within a 60 days window relative to the PET scan. Location and region of lesions as determined by the blinded PET reader will be used in all listings and tables.

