4.16.2 Primary Efficacy Variable

The primary analysis will be performed using the EAP.

The joint hypothesis is as follows:

Parexel International

Blue Earth Diagnostics Ltd

BED-PSMA-302

Statistical Analysis Plan

H_0 : CDR $\leq 36.5\%$ or PPV $\leq 62.5\%$ versus H_1 : CDR $> 36.5\%$ and PPV $> 62.5\%$

Both CDR and PPV will be displayed using a point estimate (expressed in percentage), two sided 95% CIs and a one-sided 2.5% hypothesis test for each reader.

For CDR, the two-sided 95% CIs will be exact intervals. A one-sided exact binomial test p-value will be provided for each reader for each CDR.

For PPV, the 95% CIs and p-values will be estimated using clustered binary data methodology (Section 4.16.1.3). Both CIs and binomial test p-value will be displayed for each reader.

For the study to be considered a success, the p-values for both endpoints must be statistically significant (one-sided 0.025) for at least two out of the three readers (same readers for both CDR and region level PPV). The analysis will be based on the p-value cut-offs applied to both endpoints at the interim and final analysis, if needed (Section 4.16.1.6).

In addition to the individual blinded readers, their majority CDR and PPV will be analyzed (see Section 4.14 for majority assessment).

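### As written, the majority-read rule scores regions against the imaging panel alone, so a region proven by histology but not also confirmed by the panel is TP for each matched reader and FP for their majority

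*SAP*

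**What the plan says.** SAP 4.14 defines the majority read. A region is majority-positive when two or three blinded readers mark a lesion in it, whatever its location within the region. It is then scored: "if SoT panel confirms a positive lesion, the majority would be TP, otherwise majority would become FP". The patient-level majority is defined only as positive or negative; no patient-level TP rule is given.

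SAP 4.15 names two sources of truth. One is imaging: "The imaging SoT will be matched with the blinded PET reader based on the lesion ID for each reader as identified by the SoT panel". The other is histology: "the histopathology finding by the investigator (as recorded on CRF) will be matched with the blinded PET reader finding", matched by anatomical location and used only within 60 days of the scan.

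SAP 3.2.2.3 describes the central SoT reviewers' task. Lesions are "categorized by the consensus central SoT read as positive, negative or indeterminate using all available conventional and confirmatory imaging". The reviewers receive a brief clinical summary and, beyond that, "Readers will be blinded to all other information".

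For individual readers, SAP 3.2 accepts confirmation by any of Steps 1 to 4, and Step 1 is histology. SAP 4.15 carries this to the region level for each reader. Protocol 9.1.9 states that "Histopathology remains the preferred SoT".

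SAP 4.16.2 adds that "their majority CDR and PPV will be analyzed" and refers to 4.14 for the derivation.

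**The concern.** A majority read should summarise its readers against the same reference standard that the readers face. Here the readers are scored against histology or imaging, while the majority sentence names only the panel and sends everything else to FP. The majority PPV could then fall below the PPV of all three readers for a reason unrelated to reader agreement. Anyone comparing the majority column with the reader columns would be comparing two reference standards without being told.

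The results exposed are those that use the majority together with the SoT: the majority PPV in 4.16.2, and the majority results in 4.16.3.1 to 4.16.3.4, 4.16.4.2 and 4.16.4.3. The clearest case is 4.16.3.2, where PPV is reported for regions with histology. In that subgroup the majority column would disregard the evidence that defines the subgroup.

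**Working it through.** **Which source each rule uses**

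| Situation in a region positive for all three readers | Each matched reader (SAP 3.2, 4.15) | Majority (SAP 4.14, literal) |
|---|---|---|
| Valid positive histology, panel positive | TP | TP |
| Valid positive histology, panel negative, indeterminate or no panel result | TP | FP |
| No usable histology, panel positive | TP | TP |
| No usable histology, panel not positive | FP | FP |
| Correctly placed negative biopsy, panel positive | FP if the biopsy stands (SAP 3.2.1) | TP |

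The second row is the main conflict. The last row is less certain: SAP 3.2.1 lets a correctly placed negative biopsy stand, but SAP 3.2 also makes a lesion TP if any one step confirms it.

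The second row could be common or rare. SAP 3.2.2.3 has all available imaging read centrally, so the panel may confirm many histology-proven regions. On the other hand, SAP 3.2.1 sends a lesion to imaging confirmation only when histology is missing or non-diagnostic or the biopsy missed its target, and Protocol 9.2.2.3 has the panel classify lesions when histology is not available. Some histology-proven lesions may therefore have no panel result.

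**Simple illustration.** Ten regions are positive for all three readers. Seven are TP, three of them by histology only. Each reader's PPV is 7/10 = 70%. Under the literal majority rule it is (7 − 3)/10 = 40%.

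**The plan's own figure.** The majority rule rests on no stated number, so the design value serves only as a reference point. With n = 190, a null PPV of 62.5%, a true PPV of 73.5% and one-sided 0.025, the exact binomial test rejects at 133 or more TP (70.0%). Its exact alpha is 0.0185 and its power 87.9%, which agrees with the stated >88% to within rounding.

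**Size under the literal rule.** Let h be the share of TP regions proven by histology and u the share of those that the panel does not confirm. Then

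majority PPV = 0.735 × (1 − h × u).

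The documents give neither h nor u; both are assumed over a range.

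| h | u = 25% | u = 50% | u = 100% |
|---|---|---|---|
| 10% | 71.7% | 69.8% | 66.2% |
| 20% | 69.8% | 66.2% | 58.8% |
| 30% | 68.0% | 62.5% | 51.5% |

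The smallest loss is 73.5 − 71.7 = 1.8 points and the largest 73.5 − 51.5 = 22 points. The majority PPV reaches 62.5% when h × u = 1 − 0.625/0.735 = 0.15.

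The formula counts only lost TP regions. Regions with a valid negative biopsy that the panel calls positive would offset part of the loss. It also takes the majority PPV to be 73.5% when the full SoT is used.

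**The case against.** The strongest defence is that SoT panel in 4.14 is shorthand for the whole SoT algorithm. Section 4.15 opens by pointing to Section 3.2, plans a listing that combines local histology with the central read, and makes a region TP if it holds any SoT-positive lesion. SAP 4.16.1.2.1 makes a lesion FP only when the SoT does not confirm it. Reporting a majority result for regions with histology in 4.16.3.2 makes little sense if histology is ignored. This reading is plausible and may be what was meant. But no passage defines the panel to include histology, 4.15 uses the same term for the imaging source, and 4.16.2 sends the programmer to 4.14. The SAP also states that it prevails over the protocol, so protocol wording does not settle the matter.

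A second defence is that what the panel sees is detailed in the Independent Review Charter, which is not among the documents. That stands as a limit: that the panel does not see histology is inferred from the blinding sentence.

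Several stronger readings are tempting and should not be drawn:

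- A reader might infer that every biopsy-proven region becomes a majority FP. It does so only if the panel does not also confirm it.
- A reader might infer that histology is excluded from the majority CDR. Section 4.14 gives no patient-level TP rule at all, which is a gap and not an exclusion.
- A reader might infer that nearly all secondary and exploratory results are affected. Detection rates use no SoT, and kappa and management change use no majority TP/FP status.
- A reader might take the roughly 50% concordance in Protocol Section 2 as the panel's confirmation rate. That figure compares fluciclovine with PSMA PET-positive patients at low PSA. It is not a panel-positive rate given positive histology.

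**Conclusion.** The concern holds as a conflict within the SAP. Section 4.14, followed literally, scores the majority against imaging alone, while Sections 3.2 and 4.15 score each reader against histology or imaging. The conflict follows from the text and depends on no assumed number.

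Its size does depend on assumptions. The loss of about 2 to 22 points applies only over the assumed ranges of 10 to 30% for h and 25 to 100% for u. It would be near zero if the panel confirms almost every histology-proven region.

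A reader might set these losses against the 11-point gap between 73.5% and 62.5% and conclude that the trial's success is at risk. The documents do not support that. Success requires both endpoints to be significant for the same two of three individual readers, and the majority read is no part of that test. The primary p-values and the power are unchanged. The consequence is a set of supplementary results that can mislead, and it is worth correcting before the majority tables are programmed.

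**What to change.** Replace the TP/FP sentence in SAP 4.14 with wording such as: *A majority-positive region is TP if at least one PET-positive lesion in it is SoT positive under Section 3.2 (valid histology within the 60-day window first, otherwise the panel's imaging consensus), and FP otherwise.*

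Add the matching patient-level rule for the majority CDR, for example: *A majority-positive patient is TP if at least one majority-positive region is TP under this rule.*

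If the panel-only reference was intended, say so in 4.14 and label the majority columns as scored against imaging alone.

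The cost is one or two sentences and a small change to one derivation. No new data or reads are needed, because the histology and panel results are already collected and matched to each reader under 4.15.
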